7.3 Data collection protocol

Most study data will be collected electronically. Participants who do not respond to the electronic follow-up survey invitation will have the opportunity to complete the follow-up survey either by telephone or by mail.

Baseline data: For participants who screen eligible on the recruitment website and provide their email address, we will instantly send them an email (and two reminders over a 7-day period) inviting them to complete a secured online survey to provide informed consent and complete the baseline assessments (see Table 2 below). At baseline, we will also collect email, phone number, and mailing address.

3-month follow-up data: The follow-up data collection protocol is as follows: Assessment Day -14: Mailed reminder of upcoming survey, with \$2 pre-incentive included; Day 0: First email and/or text invitation with link to online survey; Day 5: Second email and/or text invitation with link to online survey; Day 9: Third email and/or text invitation with link to online survey; Days 10 to 18: Eight attempts to complete telephone version of survey (one call per day); Day 18: Send mailed version of survey. Participants will receive an incentive of \$50 for the follow-up survey completed and an additional \$25 for returning cotinine results if asked. In addition, an extra incentive of \$10 will be provided to participants who respond to the first invitation and complete the survey online within 24 hours. Based on previous trials using these same procedures [19, 28], we expect that 80% of participants will complete assessments via web-based survey, ~2% by phone, and ~3-4% by mailed survey.

7.4 The schedule of assessments is provided in Table 2 below. Participant compensation

Participants will receive up to \$102 for participating in this study. Specifically, participants will receive compensation based on the following structure:

- \$5 for responding to each of three text message assessments of e-cigarette use, for a total of up to \$15
- \$2 in a pre-incentive letter for the 3-month follow-up
- \$50 for the 3-month follow-up survey completed in any modality
- \$10 bonus for completing the 3-month follow-survey within 24 hours of the initial email invitation

- \$25 for returning cotinine results (if asked)

8.0 SUBJECT EVALUATION

8.1 Data Collection Overview

Table 2. Schedule of assessments

Measure	# items	Screening Survey	Baseline Survey	3-mo. Follow-up Survey	Primary Purpose
Eligibility criteria	11	X			Eligibility
Demographics	10		X		Sample description
e-FTCD (severity of dependence)	6		X	X	Sample description
Tobacco/nicotine use history	9		X		Sample description
Contemplation Ladder (readiness to quit)	1		X	X	Primary outcome
Recent tobacco/nicotine use	3		X	X	Primary outcome
Saliva cotinine	n/a			X	Primary outcome
Outside tobacco treatment	2		X	X	Concomitant treatment
Treatment satisfaction	8			X	Primary outcome
Treatment adherence (tracked automatically)	n/a			X	Primary outcome
Abstinence self-efficacy	1		X	X	Exploratory
AIS cravings subscale (psychological flexibility)	9		X	X	Exploratory
Valuing Questionnaire (psychological flexibility)	10		X	X	Exploratory
Past 30-day alcohol and cannabis use	2		X	X	Exploratory
Agent Persona Instrument (avatar perceptions)	25			X	Exploratory
Adverse events				X	Safety monitoring
Total number of items		11	62	73	
Estimated duration (mins)		5-10	30-35	35-40	

8.2 Enrollment Procedures

The study recruitment website provides basic information about the study, FAQ, information about the study team and Fred Hutchinson Cancer Center (FHCC), and a portal to online screening survey.

Individuals who do not meet eligibility criteria will be sent an email notifying them that they were not enrolled and provide both the link to Smokefree.gov and the 800-QUIT-NOW phone number for cessation support.

We will use the identical enrollment method proven successful in our previous, remotely-conducted RCTs. Specifically, for participants who screen eligible on the recruitment website and provide their email address, we will instantly send them an email (and two reminders over a 7-day period) inviting them to provide informed consent and complete the baseline assessment.

To address potential fraudulent responses to web-based screening surveys, we will use the same methods used in our previous studies: CAPTCHA verification, ineligibility if the IP address was previously used or suspicious, and telephone contact by research staff if any aspect of automated data collection revealed suspicious activity (e.g., very brief survey completion times or unusual patterns in email addresses). To further deter fraudulent attempts to enter the study, no compensation will be provided for completion of the brief (< 10 min) screening and baseline surveys.

Informed Consent. Participants will be asked to review and provide consent to participate in this study before completing the baseline assessment. The informed consent will encourage individuals to contact either [name] or the project manager ([name]) with questions about the study (contact information will be provided). The informed consent will be collected and stored in the secure database behind FHCC firewall (see DSMP for additional details). Participants who complete the enrollment process will receive a copy of the informed consent via email for future reference.

Baseline Assessment. The baseline survey assesses demographics, tobacco/nicotine use history and current vaping behaviors, and use of electronic cigarettes. More details below in section 9.3. The baseline survey data will be collected and stored in a research database behind FHCC firewall (see DSMP for additional details).

Following the completion of the baseline survey and contact information form the participant will receive a text message. Once this link is clicked an email and/or a text message will be sent indicating that they are enrolled in the study.

Participants will be randomized to either the ACT on Vaping app arm or the incentivized text message control arm. The randomization algorithm will use a permuted-block design with random block sizes, with stratification by high (>5) vs. low (5 or less) readiness to quit on the Contemplation Ladder.

If applicable, the email and/or text message will provide participants with a link to the login credentials of the ACT on Vaping program. If in 3 days the participant has not logged onto the app, they will receive a text message reminder. If in 3 more days the participant has still not logged onto the app, study staff will reach out by phone to check in.

8.3 Assessments/On-Study Clinical Evaluations

A complete schedule of assessments is provided in Table 2 above. Measures collected at baseline will also be collected at the 3-month follow-up timepoint except for questions related to demographics, severity of dependence and tobacco/nicotine use history, as answers to these questions will be used to describe our study population.

All data from these assessments will be collected via web- based, telephone, or mailed surveys.

8.3.1 Eligibility and sample description

Demographics assessed at baseline will include age, assigned sex at birth, gender identity, sexual orientation, education, employment, income, number of dependents, and relationship status. The 6-item E-cigarette Fagerström Test for Cigarette Dependence (e- FTCD) [57, 58] and the 1-item Contemplation Ladder [56] will be used to assess e-cigarette dependence and readiness to quit using e-cigarettes, respectively. Nicotine and tobacco use history will be assessed using items derived from major epidemiologic surveys (e.g., BRFSS, PATH).

8.3.2 Treatment acceptability

Overall satisfaction will be assessed with a 5-point Likert-type item on the 3-month survey. The ACT on Vaping benchmark average of 3.5 falls between ratings of “somewhat satisfied” (3) and “mostly satisfied” (4).

8.3.3 Efficacy for cessation

Efficacy will be assessed via: (1) self-reported 24-hour quit attempt, (2) change in readiness to quit, and (3) cotinine-confirmed 30-day point prevalence abstinence.

Self-reported 24-hour quit attempt

Making a 24-hour quit attempt between baseline and 3-month follow-up will be assessed via self-report at the 3-month follow-up.

Change in readiness to quit

The single-item Contemplation Ladder will be used to evaluate readiness to quit. Change between baseline and 3-month follow-up will be evaluated as an indicator of efficacy.

Cotinine-confirmed 30-day point prevalence abstinence from all nicotine and tobacco

We will assess 30-day point prevalence abstinence (PPA) from all nicotine and tobacco use (excluding FDA-approved pharmacotherapies) at 3-months post-randomization, biochemically confirmed via saliva cotinine. For comparability with the only previous trial of a digital intervention for YA vaping cessation (i.e., This is Quitting trial [19]), 30-day PPA from vaping will be assessed using the following item: (“In the past 30 days, did you vape at all, even a puff of someone else’s?”), and item instructions will encourage participants to focus on all nicotine-containing vaping devices when answering. Items assessing 30-day PPA from cigarette smoking and other tobacco use will be worded similarly. We will biochemically confirm self-reported abstinence from vaping and all other non-therapeutic nicotine and tobacco products at follow-up among those who report 30-day PPA. Saliva cotinine tests (Alere iScreen) will be sent to participants via mail and they will upload photos of the test results via a secure online study portal.

Participants who report using nicotine replacement therapy (NRT) for tobacco cessation within 7 days of the scheduled date of cotinine testing will be considered abstinent without testing, since cotinine cannot distinguish e-cigarette and other tobacco use from NRT use and only method that can potentially make this distinction—urinary analysis of minor tobacco alkaloids (e.g., anatabine/anabasine) [63]—isn’t feasible in a remote trial design with national recruitment.

8.3.4 Other assessments

Use of non-study cessation treatments will be assessed at the 3-month follow-up. Comparative impact of the interventions on alcohol and cannabis co-use (e.g, number of days of use in the past month) will be explored using web-based Timeline Followback [65] to assess alcohol and cannabis use over the 30 days prior to the assessment. Acceptance of vaping triggers will be assessed using an e-cigarette version of the Avoidance and Inflexibility Scale (AIS), with a subscale measuring acceptance of bodily sensations (cravings) [30]. The AIS subscale is highly correlated [25], so to limit respondent burden, we will administer only the 9-item cravings of bodily sensations subscale, which has the strongest relationship with abstinence in previous work [25]. Values-guided action will be assessed using the 10-item Valuing Questionnaire [41], which has two subscales: Values Progress (5 items) and Values Obstruction (5 items). Change in abstinence self-efficacy will be assessed via a single-item rating of confidence in one’s ability to quit vaping, measured at baseline and 3 months. The Agent Persona Instrument (API) [42] will be administered as a treatment process measure only in the ACT on Vaping arm to assess how participants perceive the avatar. This 25-item scale has four subscales: (1) credible, (2) facilitating learning, (3) engaging, and (4) human-like. This scale is most often used in studies of online learning to assess the effectiveness of a pedagogical agent.

Adverse events will be collected by a web-based survey (on Day 21, 42, 63, and at the 3-month follow-up time point).

9.0 SUBJECT DISCONTINUATION OF ACTIVE TREATMENT

Participants can choose to discontinue their participation in this study at any time for any reason.

10.0 CONCOMITANT MEDICATIONS

Use of non-study cessation treatments will be assessed at the 3-month follow-up.

11.0 ADVERSE EVENTS

11.1 Adverse Events

This is a low-risk study testing the feasibility and preliminary efficacy of a behavioral intervention. Because this is a vaping cessation intervention, some participants may quit using nicotine and may experience the physical and psychological consequences of nicotine abstinence, such as nicotine withdrawal symptoms. As part of the informed consent procedures, participants will be informed about potential nicotine withdrawal symptoms and effects of abstinence. The intervention provides strategies designed to cope more effectively with symptoms of nicotine withdrawal. Finally, participants will be given information on pharmacotherapy for tobacco cessation (e.g., nicotine patch) and how to obtain these medications.

11.2 Collection and reporting of AEs and SAEs

Participants will be asked to report changes in their physical and mental health, especially if treatment was required. An email will be sent to participants asking about changes in their health on Day 21, 42 and 63. Adverse event reports will not be monitored in real time. The project manager will review the submitted responses weekly and will contact the participant by telephone to ask additional questions, if needed. Emergency and crisis resources will be provided to all study participants in the study consent, and at each adverse event collection time point.

Any adverse events detected during this study will be recorded in the Adverse Event Summary Form and reported as follows.

Monitoring.

Throughout the study, the project coordinator and outcome assessors will monitor participants' progress and responses to surveys for adverse events and protocol compliance. The study coordinator will complete quarterly reports on participant progress and status, any adverse events, and any protocol deviations.

Reporting.

All study staff working on the trial will be trained and required to report all unexpected and adverse events to the project coordinator and the Principal Investigator. A form will be available for this purpose. Adverse events beyond what would be expected in the course of vaping cessation will be reported to the Fred Hutch's IRB in accordance with Fred Hutch policy.

Reporting SAEs. For AEs meeting the criteria for an SAE, regardless of attribution, the study coordinator will inform the Fred Hutch IRB per their reporting guidelines and will complete and submit a NIH SAE report form within 72 hours of the reported event. Should additional information become available after the initial report, a revised report will be submitted as soon as possible.

Reporting AEs that do not meet the criteria for SAE. All reported AEs will be collected and reported via the study's electronic database. AEs that are expected will be summarized at the time of continuation review.

Reporting UEs that do not meet the criteria for AEs. The study team will report any UEs to the Fred Hutch IRB per their reporting guidelines. Fred Hutch will report the UE to the sponsor in accordance with the protocol.

Definitions

In general, unexpected events (UEs) include any event, adverse or otherwise, that was not described as part of the study risks. For this trial, an example of an unexpected event that is not adverse is a participant who has become very unhappy with trial procedures. Adverse events (AEs) are any untoward occurrence with a trial participant whether or not it can be considered to be related to their vaping cessation intervention. Examples of

adverse events in this trial could include development or worsening of depression symptoms. Serious adverse events (SAEs) include any AE that results in death, a real risk of dying, inpatient hospitalization, persistent or significant disability/incapacity, or AEs that require intervention to prevent permanent impairment or damage. In this trial, an example of a serious adverse event would be a suicide attempt.

Management of SAEs or other study risks

UEs, AEs, and SAEs will be reported to the Principal Investigator as soon as staff members are aware of them. If there is any doubt as to whether an event qualifies as a UE, AE, or SAE, staff members will be trained and encouraged to err on the side of caution – and to bring the event to the Principal Investigator’s attention for review. The PI will be responsible for managing UEs, AEs, and SAEs.

Attribution

The independent medical monitor will decide if a UE should be classified as an AE. If an event is classified as an AE, further attribution will be determined, as follows:

- Related – AEs that are definitely, probably, or possibly related to the intervention.
- Not Related – AEs that are doubtfully related or clearly not related to the intervention.

12.0 DATA AND SAFETY MONITORING PLAN

This study is a low-risk, single-site, randomized 2-arm pilot trial of a behavioral intervention for vaping cessation. Monitoring of participant safety and data quality will be overseen by an independent medical monitor, who will conduct quarterly reviews of study progress, including recruitment and retention, adverse events, and protocol adherence. A detailed DSMP is included in Appendix A.

13.0 DATA MANAGEMENT/CONFIDENTIALITY

The investigator will ensure that data collected conform to all established guidelines. Each participant is assigned a unique number to protect participant confidentiality. Only Fred Hutch IRB-approved project staff will have access to study data. All data will be maintained on a secure-access drive in permission-restricted folders only accessible to project staff. All workstations and servers are physically secured in locked offices, reside behind the Fred Hutch firewall, and fully participate in Windows NT security. The data study folder will be further safe-guarded against unauthorized access by network user login authentication controls.

In no case will participant identifiers or data be provided to any person or entity outside the IRB-approved project team. Protected health information will not be disclosed, copied, transmitted by email, or transmitted in total or in part to anyone not connected with the approved protocol and not approved by the Fred Hutch IRB. We will limit our acquisition of identifiable information to the minimum amount of information necessary to link participant data, obtain contact information for recruitment of subjects, and collect pertinent data necessary to complete the study aims.

Any data included in manuscripts or publications stemming from this study will be presented as aggregate data only, and in a way that no individual could be identified. At the end of the study, after all manuscripts are published, all identifiable files and crosswalks will be destroyed in accordance with Fred Hutch IRB policy (7 years after the end of the study). Electronic media used to store all data will be cleaned or destroyed so the data is not retrievable. As a result of these measures, we do not expect any invasion of privacy or breach of confidentiality.

When any study personnel are no longer a part of the research team, the PI will remove that person’s access to all study data and notify the Fred Hutch Information Security Officer of such action.

Online Surveys. The study database will be designed and maintained by Datatope, kept behind FHCC firewall. Only key study staff will have access to the study database system. All staff have received Human Subject

Research and HIPAA training. All data will be stored in a secure password protected computer folder, which only authorized research staff will have access to.

Mailed Surveys. Numerous safeguards will keep hard copy data secure. All hard copy data will be kept in a locked file cabinet accessible only by authorized research staff. Each participant will be assigned a code number and no personally identifiable information will be sent via mail. Should any non-study personnel gain access to the data, they will not know to whom they belong.

ACT on Vaping App. The ACT on Vaping app will be hosted internally by Fred Hutch, and utilization data will be recorded for all participants. Study IDs in the database will be unrelated to any identifying information. Data will be checked for inconsistencies, omissions, and errors. Outcome assessors will receive training in data management and confidentiality procedures and will be responsible for data entry and management.

Text Message Notifications. Participants in the ACT on Vaping arm will receive SMS text messages for 90 days. Text messages will be used to (a) prompt completion of the next session, and (b) push select intervention content to users. Notifications will be tailored to the user's level of quit readiness, with those who are not ready to quit in the next 30 days receiving values-focused, motivational messages and those who are ready to quit in the next 30 days receiving action-oriented messages (e.g., identifying and responding to triggers). All study participants will receive incentivized text message check-ins at 2 weeks, 1 month, and 2 months post-randomization. All communication with study participants will occur over Secure Sockets Layer (SSL) and no information or phone number will be shared by anyone other than IRB approved study staff.

14.0 STATISTICAL CONSIDERATIONS

14.1 Study Design

Randomized controlled 2-arm pilot trial

14.2 Primary/Secondary Endpoints/Hypotheses and Analytical Methods

We will calculate descriptive statistics (e.g., means, proportions) for the ACT on Vaping treatment group to assess treatment satisfaction (i.e., mean level of overall satisfaction with ACT on Vaping, with 3.5 on a 5-point scale being the “go” criterion). For the three cessation related-outcomes, we will evaluate differences descriptively to determine whether ACT on Vaping showed evidence of better outcomes on at least 1 of 3 efficacy endpoints as the final “go” criterion: change in readiness to quit (mean difference in Contemplation Ladder change scores ≥ 1), 24-hour quit attempts ($\geq 5\%$ difference), and cotinine-confirmed 30-day point prevalence abstinence from all nicotine/tobacco products at 3 months ($\geq 5\%$ difference). Given that pilot and feasibility trials are not appropriate designs for testing hypotheses regarding the efficacy of interventions [66, 67], we will focus on descriptive differences as an alternative to hypothesis testing. Similarly, since a single effect size derived from a small sample is an inherently unreliable estimate of the true intervention effect size [67], we aimed to reduce the likelihood of early abandonment of a potentially promising treatment by requiring evidence of a clinically meaningful effect on one of three cessation-related outcomes as the “go” criterion for efficacy.

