14.5 Missing Data

Participants with missing tobacco use data will be considered non-abstinent [73] in the primary analysis. We will also report the results of sensitivity analyses using complete case analysis of those providing follow-up data. If there is a substantially differential rate of missing data (either self-report or cotinine analytic results) across arms, we will use complete case analysis in the primary outcome analysis instead of missing=tobacco use.

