3.5 Data analysis plan

To address Sex as a Biological Variable, we will explore whether outcomes described below are associated with sex assigned at birth. If they are, that variable will be added to the relevant models. Primary analyses will be conducted as described below:

To evaluate the go/no-go criteria for the pilot trial, we will calculate descriptive statistics (e.g., means, proportions) for the ACT on Vaping treatment group to assess treatment satisfaction (i.e., mean level of overall satisfaction with ACT on Vaping, with 3.5 on a 5-point scale being the “go” criterion). For the three cessation related-outcomes, we will evaluate differences descriptively to determine whether ACT on Vaping showed evidence of better outcomes on at least 1 of 3 efficacy endpoints as the final “go” criterion: change in readiness to quit (mean difference in Contemplation Ladder change scores ≥ 1), 24-hour quit attempts ($\geq 5\%$ difference), and cotinine-confirmed 30-day point prevalence abstinence from all nicotine/tobacco products at 3 months ($\geq 5\%$ difference). Given that pilot and feasibility trials are not appropriate designs for testing hypotheses regarding the efficacy of interventions [5, 6], we will focus on descriptive differences as an alternative to hypothesis testing. Similarly, since a single effect size derived from a small sample is an inherently unreliable estimate of the true intervention effect size [6], we aimed to reduce the likelihood of early abandonment of a potentially promising treatment by requiring evidence of a clinically meaningful effect on one of three cessation-related outcomes as the “go” criterion for efficacy.

Missing data. Participants with missing nicotine use data will be considered non-abstinent [6] in the primary analysis. We will also report the results of sensitivity analyses using complete case analysis of those providing follow-up data. If there is a substantially differential rate of missing data (either self-report or cotinine analytic results) across arms, we will use complete case analysis in the primary outcome analysis instead of missing=vaping/smoking.

4 Quality assurance plan

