5.3 Report of changes or amendments to the protocol

The PI will apply to the Fred Hutch IRB for a modification to request changes or amendments to the protocol. When approved, the modification will serve as the official report of the changes or amendment. Major changes to the protocol will be pre-approved by the NIDA Program Officer.

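### The Ladder go criterion uses the raw difference in mean change and leaves out baseline Ladder and readiness stratum, so a chance baseline difference between arms can decide whether it is met

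*Combined protocol and SAP*

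**What the plan says.** Section 14.2 defines the Ladder criterion as "change in readiness to quit (mean difference in Contemplation Ladder change scores" of at least 1. Section 3.5 of the Data and Safety Monitoring Plan (DSMP, Appendix A) repeats it as "mean difference in Contemplation Ladder change scores", with the same cut. The Synopsis, section 1.0, section 4.1.1 and DSMP 1.2 restate it. The comparison is descriptive and no model is named.

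Table 2 in section 8.1 lists "Contemplation Ladder (readiness to quit" in both the baseline and the 3-month survey. Sections 8.2 and 14.4 randomise in permuted blocks "with stratification by high (>5) vs. low (5 or less) readiness to quit on the Contemplation Ladder". The baseline score and the stratum therefore exist for everyone before assignment.

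The only adjustment variable mentioned is sex assigned at birth, to be examined for association with outcome; DSMP 3.5 says "If they are, that variable will be added to the relevant models", but specifies no models. Section 7.3 says "we expect that 80% of participants will complete assessments via web-based survey, ~2% by phone, and ~3-4% by mailed survey". The rule in section 14.5, "Participants with missing tobacco use data will be considered non-abstinent", concerns tobacco use. No rule is given for a missing 3-month Ladder score.

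**The concern.** Subtracting the baseline score in full is right only if follow-up rises one point for each baseline point. When that slope is below 1, the arm that starts lower shows the larger mean change even if the app does nothing. With 30 per arm and a hard cut at 1 point, meeting the criterion then depends partly on the direction of a chance imbalance.

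Stratifying at 5 balances the two halves of the scale, but not the scores within each half, and loss to follow-up adds further imbalance. Because one efficacy criterion of three is enough, the Ladder alone can supply the efficacy part of a go. The design uses readiness to balance the arms; the analysis then ignores it.

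**Working it through.** **Plan's own figure.** There is none to reproduce. The 60 participants rest on a 15 to 30 per arm convention (section 14.3), with no SD, alpha or power stated.

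**Inputs.**
- From the earlier single-arm pilot (section 2.3; 22 cigarette smokers): baseline Ladder mean 6.2, SD 2.7; mean gain 2.1, SD of change 3.0.
- Follow-up: 80% + 2% + 3 to 4% = 85 to 86%, so 30 × 0.855 ≈ 26 per arm.
- Assumed: follow-up SD 2.3, range 2.0 to 3.0; block sizes 2, 4 and 6; loss at random.

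**Step 1: pull of an imbalance.** The slope of follow-up on baseline is (SD₀² + SD₁² − SD_change²) / (2·SD₀²). At SD₁ = 2.3 it is (7.29 + 5.29 − 9.00)/14.58 = 0.25. Each point by which the app arm starts lower adds 1 − slope ≈ 0.75 point to the raw difference. The pull is 0.84 at SD₁ 2.0, 0.62 at 2.7 and 0.50 at 3.0.

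**Step 2: what stratification already does.** Ignoring stratification, the raw SE is 3.0·√(2/30) = 0.775. At SD₁ = 2.7 (correlation 0.383) the adjusted SE is 2.7·√(1 − 0.383²)·√(2/30) = 0.644. In an unbounded normal simulation of the design at SD₁ = 2.7, the variance is 0.587 raw without stratification, 0.493 raw with it and 0.425 adjusted. Stratification thus removes (0.587 − 0.493)/(0.587 − 0.425) = 58% of the loss at full follow-up.

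**Step 3: simulated design.** Scores are rounded and clipped to 0–10, matched to the four pilot figures, and randomised within stratum. Raw is the difference in mean change. Adjusted is the arm coefficient from least squares on arm, baseline and stratum. Go means at least 1. With no true effect:

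| Follow-up SD | 30 per arm: variance | Ladder go, raw / adjusted | About 26 per arm: variance | Ladder go, raw / adjusted |
|---|---|---|---|---|
| 2.0 | −28% | 5.0% / 2.7% | −35% | 7.0% / 3.3% |
| 2.3 | −21% | 6.2% / 4.3% | −25% | 8.2% / 5.5% |
| 2.7 | −12% | 7.2% / 6.1% | −15% | 9.4% / 7.9% |
| 3.0 | −6% | 8.0% / 7.3% | −8% | 10.3% / 9.5% |

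At SD 2.3 the SEs are 0.65 raw and 0.58 adjusted at full follow-up, and 0.73 and 0.63 with loss. In the unbounded model at full follow-up, the variance gain runs from −36% at SD 2.0 to −1% at SD 3.5, which is no useful gain.

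**Step 4: by direction of imbalance, with loss.** The SD of the baseline difference is 0.50 (0.40 at full follow-up). It exceeds 0.5 point in 15 to 16% of trials each way (about 10% each way at full follow-up). Chance of a Ladder go in those trials:

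| | Raw, app arm lower / higher | Adjusted, lower / higher |
|---|---|---|
| No effect, SD 2.3 | 25% / 0.6% | 6% / 6% |
| No effect, SD 3.0 | 21% / 4% | 10% / 10% |
| True effect 1, SD 2.3 | 80% / 22% | 51% / 50% |
| True effect 1, SD 3.0 | 65% / 34% | 50% / 48% |

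Over all trials, the two methods disagree on the Ladder criterion in 16% at a true 1-point effect (range 8% to 20%) and in about 5 to 6% under no effect.

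**Step 5: the any-of-three decision.** With 30 per arm, a 5% difference means at least 2 participants (0.05 × 30 = 1.5). Under no effect, exact binomials at assumed rates of 40% quit attempts and 10% abstinence give false passes of 34.6% and 25.6%. Treating the endpoints as independent, at least one pass has chance 1 − 0.918 × 0.654 × 0.744 = 55.3% with the raw Ladder rule and 1 − 0.945 × 0.654 × 0.744 = 54.0% with the adjusted one. Other assumed rates (20% and 5%; 60% and 15%) also give a fall of 1 to 2 points, from about 48% and 58%. The efficacy decision changes in about 3 to 4% of null trials.

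**The case against.** The raw difference is unbiased, simple and defensible in a pilot that disclaims hypothesis tests and sets a deliberately lenient rule. Stratification already does more than half the work. The large contrasts by direction apply only to the 20 to 31% of trials with an imbalance above 0.5 point. The 16% disagreement arises at an effect equal to the cut, where either method passes half the time, so it is not an error rate. For an effect clearly above the cut the gain is slight: at a true 1.5 points, follow-up SD 2.7 and 85.5% follow-up, go is 74.5% raw and 76.2% adjusted. An SD of 2.3 is more favourable to adjustment than the pilot's baseline SD of 2.7 would be. The 3 to 4% is also an upper limit, because satisfaction of at least 3.5 and the completed FDA Q-submission are required too, and positively related endpoints would make the Ladder decisive less often.

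All of this stands as a limit on size. It does not favour the raw contrast: an adjusted mean difference is equally descriptive, on the same scale with the same cut. Reporting it only as a sensitivity result would leave the criterion tied to the less precise estimate. Informative dropout is a separate matter that adjustment does not settle, and the sex sentence in DSMP 3.5 can be handled independently.

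**Conclusion.** The point holds, as an improvement to consider rather than the correction of an error. The Ladder criterion ignores a baseline score and a stratum held for everyone, and its result depends partly on which arm started lower. With the expected loss, adjustment lowers the variance by 25% at follow-up SD 2.3, and by 8% to 35% across SD 3.0 to 2.0. It removes nearly all dependence on the direction of imbalance. It does not make a go more likely: at a true 1-point effect the average chance is 50% either way. The effect on the overall decision is small.

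Confidence is medium. The follow-up SD is assumed, the other SDs come from 22 smokers using a different programme (the number behind the change SD is not stated), and all loss was simulated at random.

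**What to change.** In the six places that state the criterion (Synopsis, 1.0, 4.1.1, 14.2, DSMP 1.2 and DSMP 3.5), call it the baseline-adjusted difference between arms in mean Ladder change, with the cut still at 1. In 14.2 and DSMP 3.5 add:

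> The adjusted difference (ACT on Vaping minus control) is the arm coefficient from a linear model of the 3-month Ladder score on arm, continuous baseline Ladder score and readiness stratum (>5 vs 5 or less), in all randomised participants with a 3-month Ladder score, analysed as assigned. The unadjusted difference and the number with Ladder data per arm are reported alongside. No hypothesis test is performed.

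The endpoint wording in the Synopsis, 4.3.2 and DSMP 1.3 can stay: once baseline is in the model, the arm coefficient is the same for 3-month score and for change. The two binary criteria are unaffected. As a separate, minor clean-up, DSMP 3.5 could state that sex assigned at birth is summarised descriptively by arm and does not enter the go/no-go estimates.

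The cost is wording and an IRB modification, with no new data. DSMP 5.3 adds that "Major changes to the protocol will be pre-approved by the NIDA Program Officer", which applies if this counts as major. The change should be made before outcome data are seen; afterwards, choosing between two estimates that may fall either side of 1 would be discretionary.
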